6. SYNOPSIS

Study Title: A Multicenter, Randomized, Parallel Group, Double Blind, Multiple Dose, Placebo Controlled Study to Assess the Efficacy and Safety of MNK-1411 in Male Subjects 4 to 8 Years of Age With Duchenne Muscular Dystrophy	
Protocol Number: MNK14112096	Type: Phase 2
Condition/Disease:	Duchenne Muscular Dystrophy
Approximate Number of Subjects: 132	Approximate Duration of Subject Participation: 24 weeks for the Blinded Treatment Period, Open Label Extension Period until study termination.
Approximate Number of Study Centers: 50 globally	Approximate Duration of Study: The Blinded Treatment Period portion of the study is estimated to be 3 years.
Design: This is a multicenter, double blind, placebo controlled, multiple dose study to examine the safety and efficacy of MNK-1411 in male subjects 4 to 8 years of age (inclusive) with Duchenne Muscular Dystrophy (DMD). Approximately 150 subjects will be screened in order to randomize 132 (44 per treatment group). Following a screening period of up to 28 days, subjects will be randomized on a 2:2:1:1 basis to receive 24 weeks of treatment with 2 weight based doses of MNK-1411 or volume matched placebo administered 2x/week. Subjects will return to the clinic for visits at 4, 8, 12, 16, and 24 weeks after their first dose of study drug. Subjects who complete the 24-week Blinded Treatment Period will be eligible to enter an Open Label Extension Period where all subjects will receive treatment with MNK-1411. Participation in the Open Label Extension Period will continue until the subject chooses to discontinue treatment, the investigator feels that treatment is no longer indicated, MNK-1411 is approved and marketed, or the sponsor ceases development of this compound for DMD. All subjects will complete a 2-week drug taper after their last full dose of study drug and a follow-up visit 28 (\pm 7) days after their last full dose of study drug. The taper is not required for any subject who has a hypersensitivity reaction to the study drug.	
Objectives: Primary Objective To determine the effect of MNK-1411 on motor function in subjects with DMD. Secondary Objectives To assess the effect of MNK-1411 on motor skills and strength. To determine the safety and tolerability of MNK-1411 in subjects with DMD. Exploratory Objectives 	

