
• Treatment A: MNK-1411 0.5 mg (0.5 mL, for subjects weighing more than 20 kg) or 0.4 mg (0.4 mL, for subjects weighing less than or equal to 20 kg) administered SC 2 times per week (2x/week) (administered on either Sunday and Wednesday, Monday and Thursday, Tuesday and Friday, or Wednesday and Saturday).• Treatment B: MNK-1411 0.25 mg (0.25 mL, for subjects weighing more than 20 kg) or 0.2 mg (0.2 mL, for subjects weighing less than or equal to 20 kg) administered SC 2x/week (administered on either Sunday and Wednesday, Monday and Thursday, Tuesday and Friday, or Wednesday and Saturday).• Treatment C: Volume matched placebo (0.5 mL for subjects weighing more than 20 kg or 0.4 mL for subjects weighing less than or equal to 20 kg) administered SC 2x/week (administered on either Sunday and Wednesday, Monday and Thursday, Tuesday and Friday, or Wednesday and Saturday).• Treatment D: Volume matched placebo (0.25 mL for subjects weighing more than 20 kg or 0.2 mL for subjects weighing less than or equal to 20 kg) administered SC 2x/week (administered on either Sunday and Wednesday, Monday and Thursday, Tuesday and Friday, or Wednesday and Saturday).	
During the Open Label Extension Period, subjects will be treated with MNK-1411 at the dose administered during the Blinded Treatment Period. If a subject requires a switch in dose (eg, switch to low dose due to being unable to tolerate high dose, or switch to high dose based on increased weight [eg, as subject grows with age]), the investigator should consult with the medical monitor. No switches in dose are permitted during the Blinded Treatment Period.	
All subjects will complete a 2-week taper after their last full dose of study drug. In the first week of the taper, each subject will receive one-half of their original dose administered 2x/week for 1 week, followed by one-half of their original dose administered 1 time per week for 1 week. The taper is not required for any subject who has a hypersensitivity reaction to the study drug.	
Efficacy Evaluations:	
The following efficacy assessments will be evaluated: 10 Meter Walk/Run, North Star Ambulatory Assessment (NSAA), Time to Climb 4 Standardized Stairs, Time to Stand from A Supine Position, quantitative muscle testing, pulmonary function tests, and biomarkers.	
Pharmacokinetic and Pharmacodynamic Evaluations:	

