Unless otherwise specified, all statistical tests will be two-sided with a significance level of 0.05. Summary statistics will be provided for all study variables with descriptive statistics (number of observations, mean, SD, median, minimum, and maximum) for numerical (or continuous) variables, and frequency and percentages will be calculated for categorical variables. All data will be summarized by treatment groups as appropriate. The 2 placebo groups will be combined for all analyses. Data summary and analyses will be performed with SAS 9.4 or higher.

The primary efficacy endpoint is a change from baseline in 10 Meter Walk/Run time at Week 24. The primary statistical analysis method for the endpoint will be performed using an analysis of variance (ANOVA) model with treatment as a main factor and baseline value as a covariate.

The secondary efficacy endpoints will be analyzed using the same statistical method as that for the primary efficacy endpoint.

Additional exploratory analyses [REDACTED]
[REDACTED]

Pharmacokinetic Analysis

Population PK analysis for MNK-1411 will be conducted using nonlinear mixed effects modeling.

Safety Analysis

Treatment-emergent adverse events and serious adverse events will be summarized using the appropriate version of MedDRA by preferred term within system organ class. Other safety data will be listed and summarized descriptively or graphically, as appropriate.

Study Title: A Multicenter, Randomized, Parallel Group, Double Blind, Multiple Dose, Placebo Controlled Study to Assess the Efficacy and Safety of MNK-1411 in Male Subjects 4 to 8 Years of Age With Duchenne Muscular Dystrophy

Protocol Number: MNK14112096	Type: Phase 2
Condition/Disease:	Duchenne Muscular Dystrophy

Quality of Life/Health Outcomes Analysis

The PODCI (sport and physical functioning domain and transfer/basic mobility domain) will be summarized at baseline and each study visit. Change from baseline to Weeks 4, 8, 12, 16, and 24 in PODCI domains also will be summarized. The change from baseline data will be analyzed using the same methods as those used for the primary efficacy endpoint.

Open Label Extension Analysis

In the Open Label Extension Period, efficacy data will be summarized at each visit. Safety data will also be summarized as appropriate.

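### Weight at the 20 kg cut sets the active dose and is known before the first injection, yet the stated efficacy model does not adjust for it: a small, nearly free gain in precision is left out

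*Combined protocol and SAP*

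**What the plan says.** Synopsis, Design: subjects are randomised 2:2:1:1 to "2 weight based doses of MNK-1411 or volume matched placebo administered 2x/week".

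Synopsis, Study Drug and Treatment Administration: the 20 kg cut fixes what is injected.
- Treatment A: 0.5 mg for "subjects weighing more than 20 kg) or 0.4 mg (0.4 mL, for subjects weighing less than or equal to 20 kg".
- Treatment B: "MNK-1411 0.25 mg (0.25 mL, for subjects weighing more than 20 kg) or 0.2 mg" at or below the cut.
- Treatment C: "Volume matched placebo (0.5 mL for subjects weighing more than 20 kg or 0.4 mL" at or below the cut. Treatment D does the same with 0.25 and 0.2 mL. In these two groups weight sets a volume, not a dose.
- The assignment then holds for the blinded phase: "No switches in dose are permitted during the Blinded Treatment Period".

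Synopsis, Efficacy Analysis: the primary endpoint, Week 24 change in 10 Meter Walk/Run time, is analysed with an "analysis of variance (ANOVA) model with treatment as a main factor and baseline value as a covariate". The model carries over: "The secondary efficacy endpoints will be analyzed using the same statistical method as that for the primary efficacy endpoint". The PODCI change scores use it too. The two placebo groups are pooled.

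The visible text has no weight term in these models, no stratification of randomisation by weight and no estimate by weight band. The exploratory analyses are redacted. Population PK modelling is planned, as is an exposure-response analysis of selected Week 4 endpoints.

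**The concern.** Weight is measured before treatment, must be available to choose the first volume, and partly defines what a boy on active drug receives. In boys aged 4 to 8 it may also be related to change in walking time. A baseline variable of that kind is a natural covariate. If it predicts the outcome beyond baseline walk/run time, leaving it out has two consequences. The variation it explains stays in the error term, and a chance difference in weight between a dose group and placebo moves the estimate without correction. At stake is efficiency in a trial with 37 expected completers per group, not the validity of the test.

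**Working it through.** **Inputs from the Synopsis (Sample Size, Efficacy Analysis).** 37 completers per group; 1 s difference; 80% power; "all statistical tests will be two-sided with a significance level of 0.05"; about 15% dropout; 44 per group; 132 in total.

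**Inputs that are assumed.** The SD, the share of boys in each band and the band difference in outcome are not given.

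**1. The plan's own figures.** Dropout: 37 / 0.85 = 43.5, rounded up to 44; 3 x 44 = 132. This reproduces. The 80% power cannot be checked independently without an SD. Solving for the SD that gives 80% power with 37 per group, 1 s and two-sided 0.05 yields 1.515 s (two-sample t test) or 1.535 s (normal approximation). I use 1.515 s.

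**2. Precision gained from a weight-band term.** Let g be the band difference in Week 24 change that remains after adjustment for treatment and baseline walk/run time, with half the boys in each band.
- Share of variance explained: R² = 0.25 x g² / 1.515²
- Residual SD = 1.515 x sqrt(1 - R²)
- Power recomputed by noncentral t, 37 per group, 1 s difference.

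| g (s) | R² | Residual SD (s) | Power |
|---|---|---|---|
| 0 | 0 | 1.515 | 79.98% (one degree of freedom spent) |
| 0.25 | 0.7% | 1.510 | 80.3% |
| 0.5 | 2.7% | 1.494 | 81.1% |
| 0.75 | 6.1% | 1.468 | 82.4% |
| 1.0 | 10.9% | 1.430 | 84.3% |

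For continuous weight, with an assumed partial correlation rho with the outcome, residual SD = 1.515 x sqrt(1 - rho²). Power is 80.4% at rho 0.1, 81.6% at 0.2 and 83.6% at 0.3.

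**3. Chance imbalance.** With 44 per group, unstratified randomisation and half the boys in each band, the SD of the difference in band proportions is sqrt(2 x 0.25 / 44) = 0.107. The chance of a difference of at least 10 points is about 35% (normal approximation). Such an imbalance shifts the estimate by 0.10 x g: 0.05 s at g = 0.5 and 0.10 s at g = 1.0. The standard error of the treatment difference is 1.515 x sqrt(2/37) = 0.352 s, so the shift is 14% to 28% of one standard error.

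**4. Does a weight main effect change what is estimated?** In 4,000 simulated trials of 37 per group, with true effects of 0.7 s and 1.3 s in the two bands (average 1.00 s), the mean estimate was 1.01 s with and without the weight term. The spread fell from 0.361 to 0.358. The estimand is unchanged; only precision moves.

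**5. What estimates by band could show.** With half the boys in each band, there are 37 / 2 = 18.5 completers per group per band.
- Standard error = 1.515 x sqrt(2/18.5) = 0.498 s; 95% CI half-width about 1.0 s; power for 1 s within a band about 50%.
- With a 30/70 split, the smaller band has 11.1 per group: half-width about 1.3 s, power about 32%.
- A 1 s treatment-by-band interaction has standard error 1.515 x sqrt(2/18.5 + 2/18.5) = 0.704 s and power of about 29%.

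**The case against.** The strongest reply is that there is no error here. Each arm is defined as a weight-based regimen, so the regimen is the treatment and its contrast with placebo is what the trial sets out to estimate. Randomisation protects that contrast, and the test already allows for chance imbalance. The gain is small and rests on assumed band differences, the largest of which equals the whole target effect. Baseline walk/run time is already in the model and may absorb much of what weight would add. All of this stands, and it limits the point to an optional improvement. It does not remove the point, because the covariate is already in hand and adding it costs almost nothing.

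A reader might infer four stronger things that the documents do not support.
- *That the missing term causes each arm's effect to average two doses, or biases it.* The averaging comes from the regimen; a weight main effect leaves it in place (step 4).
- *That weight is ignored throughout.* The exploratory analyses are redacted and the PK modelling may use weight; the abbreviations list includes the subject's weight in kg. The statement holds only for the visible efficacy models.
- *That the spread of dose per kg argues for a two-level term.* Much of that spread lies within bands: Treatment A gives 0.4/20 = 0.020 mg/kg at 20 kg and 0.5/25 = 0.020 mg/kg at 25 kg. A band factor does not capture it.
- *That estimates by band would show whether both bands benefit.* At a half-width of about 1 s they cannot.

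**Conclusion.** The stated primary model and its copies leave out a pre-treatment variable that sets the active dose and costs nothing to collect. The planned analysis is valid and unbiased without it. The loss is modest: power of 80% against 80.3% to 84.3% for residual band differences of 0.25 to 1.0 s, and essentially nothing if there is no difference. These figures assume an SD of about 1.5 s (implied, not stated), an even split between bands, and a difference that survives adjustment for baseline walk/run time. The imbalance figures also assume unstratified randomisation. The visible text shows no stratification by weight; if weight band is a stratification factor described elsewhere, the case for including it in the model is stronger. This is a minor efficiency suggestion.

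**What to change.** Before unblinding, add one sentence to the statistical section naming baseline weight as a covariate in the primary model and in the models for the secondary endpoints and PODCI. Choose the form in advance: continuous weight, or the 20 kg band, with the band preferred if randomisation is stratified by it. State in the same place whether it is.

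Optionally, report each dose-versus-placebo estimate by weight band with its 95% CI. Label these descriptive, and note the half-width of about 1 s per band, so that no one reads them as establishing benefit, or its absence, within a band.

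The cost is one sentence and one degree of freedom, with no new data. No change to dosing is proposed.

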CLINICAL STUDY PROTOCOL

A Multicenter, Randomized, Parallel Group, Double Blind, Multiple Dose, Placebo Controlled Study to Assess the Efficacy and Safety of MNK-1411 in Male Subjects 4 to 8 Years of Age With Duchenne Muscular Dystrophy

NCT03400852

Summary adjusted for disclosure

Protocol Number: MNK14112096

Date of Original Protocol: 22 August 2017

Date of Protocol Amendment 1: 16 November 2017

Date of Protocol Amendment 2: 22 August 2018

Date of Protocol Amendment 3: 23 May 2019

Mallinckrodt ARD LLC
[name]
[name]
United States of America

PROTOCOL AMENDMENT 3

SUMMARY OF CHANGES

In order to accommodate subject needs, Protocol Amendment 3 was developed primarily to extend the Open Label Extension Period beyond Week 52 (to continue until the subject chooses to discontinue treatment, the investigator feels that treatment is no longer indicated, MNK-1411 is approved and marketed, or the sponsor ceases development of this compound for Duchenne Muscular Dystrophy [DMD]). Open label visits will continue every 12 weeks, with dispensing of study drug every 12 weeks. Along with this change, text has been added stating that if a subject requires a switch in dose during the Open Label Extension Period (eg, switch to low dose due to being unable to tolerate high dose, or switch to high dose based on increased weight [eg, as subject grows with age]), the investigator should consult with the medical monitor. Since subjects will be participating in the study longer, measurements of height have been added to all study visits.

Additional major protocol changes are summarized below and a more comprehensive [Summary of Changes](#) document, including minor protocol changes, is provided separately:

- To accommodate the needs of study sites in Israel, the combination of Sunday and Wednesday has been added as possible visit and/or dosage administration days.
- Text has been added specifying that subjects who have a hypersensitivity reaction to the study drug are not required to undergo the 2-week taper, or standard cosyntropin stimulation test (250 µg) at the follow-up visit.
- Varicella zoster testing has been added along with an inclusion criterion (Inclusion criterion 6) requiring subjects to test positive prior to study entry (since such infections may be serious in patients who are immunosuppressed).
- Pharmacokinetic analysis text has been corrected.

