- A mandatory study drug taper has been added. All subjects will complete a 2-week taper after their last full dose of study drug. In the first week of the taper, each subject will receive one-half of their original dose administered 2 times per week for 1 week, followed by one-half of their original dose administered 1 time per week for 1 week.
- All subjects will have a standard cosyntropin stimulation test (250 µg) at their Follow-up Visit.
- References to “legally authorized representative” have been removed from the protocol. Only a parent or legal guardian can give consent for subjects to participate.
- The listing of chemistry laboratory tests in Attachment 1, [Section 32.1](#) has been clarified (creatinine updated to creatine phosphokinase).

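### Does the mandatory taper have a usable reference dose for a boy whose dose was switched in the open-label extension?

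*Combined protocol and SAP*

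**What the plan says.** Section 6 (Synopsis), Study Drug and Treatment Administration, requires a taper of every subject: "All subjects will complete a 2-week taper after their last full dose of study drug". The only exception is a hypersensitivity reaction. In week 1, "each subject will receive one-half of their original dose administered 2x/week for 1 week"; in week 2, "followed by one-half of their original dose administered 1 time per week for 1 week".

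The same section gives four full doses of MNK-1411: 0.5 mg (above 20 kg) or 0.4 mg (20 kg or less) for Treatment A, and 0.25 mg or 0.2 mg for Treatment B. The extension starts at the blinded-period dose. If a switch is needed, the investigator should consult the medical monitor; the examples are "switch to low dose due to being unable to tolerate high dose, or switch to high dose based on increased weight". For the blinded period the rule is plain: "No switches in dose are permitted during the Blinded Treatment Period".

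The Design paragraph of the synopsis sets the follow-up visit 28 (±7) days after the last full dose. The Summary of Changes for Amendment 1 states "All subjects will have a standard cosyntropin stimulation test" at that visit; Amendment 3 exempts subjects with a hypersensitivity reaction.

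**The concern.** The taper and the switch provision entered the protocol at different times. Amendment 1 (16 November 2017) introduced the taper, already in the words "each subject will receive one-half of their original dose administered 2 times per week for 1 week". Amendment 3 (23 May 2019) reports that "text has been added stating that if a subject requires a switch in dose during the Open Label Extension Period". The current synopsis carries both, and nothing supplied links the word *original* to either the pre-switch or the post-switch dose.

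Two sites could therefore halve different doses for the same boy. If *original* means the blinded-period dose, a boy stepped down from high to low within one weight band would get taper injections as large as his current full dose. A boy stepped up from low to high would drop to a quarter or less of his current weekly dose in week 1. In the step-down case it would also be less clear which injection counts as the last full dose, and that dose times the follow-up visit and its cosyntropin test.

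**Working it through.** The documents state no taper dose in mg, so there is no figure to reproduce. The inputs are the four full doses and the taper schedule (two injections, then one) in Section 6.

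**Taper size.** Let *o* be the full dose before the switch and *c* the full dose after it. Current weekly dose = 2*c*.

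- Blinded-period reading: week 1 = 2 × (*o*/2) / (2*c*) = *o*/(2*c*); week 2 = (*o*/2) / (2*c*) = *o*/(4*c*).
- Last-full-dose reading: week 1 = 2 × (*c*/2) / (2*c*) = 50%; week 2 = (*c*/2) / (2*c*) = 25%, for every boy.
- Fold difference = larger of *o* and *c* divided by the smaller.

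| Switch (mg) | Type | Taper injection, *o*/2 vs *c*/2 (mg) | Fold | Blinded-period reading, weeks 1 and 2 (% of current weekly dose) |
|---|---|---|---|---|
| 0.5 to 0.25 | high to low, same band | 0.25 vs 0.125 | 2.0 | 100, 50 |
| 0.4 to 0.2 | high to low, same band | 0.20 vs 0.10 | 2.0 | 100, 50 |
| 0.4 to 0.25 | high to low, crossing 20 kg | 0.20 vs 0.125 | 1.6 | 80, 40 |
| 0.25 to 0.5 | low to high, same band | 0.125 vs 0.25 | 2.0 | 25, 12.5 |
| 0.2 to 0.4 | low to high, same band | 0.10 vs 0.20 | 2.0 | 25, 12.5 |
| 0.2 to 0.5 | low to high, crossing 20 kg | 0.10 vs 0.25 | 2.5 | 20, 10 |
| 0.4 to 0.5 | weight band only | 0.20 vs 0.25 | 1.25 | 40, 20 |
| 0.2 to 0.25 | weight band only | 0.10 vs 0.125 | 1.25 | 40, 20 |

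The largest total difference, over three injections, is 3 × 0.10 = 0.30 mg against 3 × 0.25 = 0.75 mg. The 2.5-fold figure needs a change of level and of weight band together. The last two rows assume that a move to the heavier band's dose of the same treatment counts as a switch.

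**Follow-up timing.** This matters only for a same-band step-down on the blinded-period reading. The permitted dosing days are pairs spaced 3 and 4 days apart. Count the last full dose as day 0 and keep those days:

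- Last full dose on the first day of a pair: taper injections on days 3 and 7, then on day 10 or 14.
- Last full dose on the second day of a pair: days 4 and 7, then day 11 or 14.

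The final taper injection thus falls on day 10, 11 or 14. The visit at day 28 comes 28 − 14 = 14 to 28 − 10 = 18 days later. With the ±7-day window the range is 21 − 14 = 7 to 35 − 10 = 25 days. On the last-full-dose reading each taper injection is half the current dose, so the anchor stays clear.

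**Placebo boys.** Randomization is 2:2:1:1, so (1 + 1)/6 = one-third, or 44 of 132, start on placebo. All who enter the extension receive MNK-1411. Half of a blinded-period dose, taken literally, is 0 mg of active drug for them, even with no switch. That reading works for them only if *dose* is recast as the matched volume level, which the text does not say.

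**Boys for whom the readings agree.** A boy on active drug who never switches has *o* = *c*. So does any boy who stops during the blinded period.

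**The case for a change.** The case for a change is that the gap is foreseeable. Boys enrol at 4 to 8 years, the dose depends on a 20 kg threshold, the extension is open-ended, and the protocol itself expects switches with growth. The blinded-period reading is not fanciful: the extension starts from that dose and then permits departures from it. The medical-monitor sentence covers the switch and does not mention the later taper. A defining phrase would cost very little.

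Much of this stands. The term is undefined in the supplied text, the arithmetic is right, and the taper is compulsory for nearly everyone. It does not follow that sites would be left without guidance. Only the amendment summaries, abbreviations and synopsis are available here. The amendment summaries cite full sections on eligibility, concomitant treatment and laboratory tests, and sites work from the full protocol. A synopsis is not where a dosing term is normally defined. The medical monitor should already know of each boy who has switched, so a query about his taper has an obvious place to go.

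**Conclusion.** No change to the plan follows. This is a gap in synopsis wording that the people running the trial can be expected to fill sensibly. The neighbouring sentence, which starts the taper after the last full dose, supplies a reading that holds together for every boy. The competing reading removes the week 1 reduction after a same-band step-down and fails, taken literally, for the one-third randomized to placebo.

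The difference between readings is 1.25-fold for a weight-band change alone, 1.6-fold or 2.0-fold for most level switches, and 2.5-fold at the extreme. It concerns boys who switch in the extension, whose number is not given, and boys who move from placebo to MNK-1411. It does not touch the sample size, the blinding or the primary analysis: switches are barred before Week 24, and the synopsis plans summaries of extension data.

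This conclusion assumes that the sections not supplied do not contradict the synopsis. Reconciling the taper and switch sentences is a matter of drafting. Which dose the taper should refer to is for the sponsor's clinical team, and no view on it is taken here.

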The pharmacokinetics (PK) of MNK-1411 in DMD patients will be characterized using population PK modeling with sparse PK sampling implemented in this study. The exposure response (selected efficacy and/or safety endpoints at Week 4) relationship will be explored.	
Safety Evaluations:	
The following safety assessments will be evaluated: adverse events, medical history, physical examinations, concurrent medical conditions, height, weight, clinical laboratory tests, vital signs, electrocardiograms, and antidrug antibodies.	

Study Title: A Multicenter, Randomized, Parallel Group, Double Blind, Multiple Dose, Placebo Controlled Study to Assess the Efficacy and Safety of MNK-1411 in Male Subjects 4 to 8 Years of Age With Duchenne Muscular Dystrophy

Protocol Number: MNK14112096	Type: Phase 2
Condition/Disease:	Duchenne Muscular Dystrophy

Quality of Life/ Health Outcome Evaluations:

The following quality of life /health outcome assessment will be evaluated: Pediatric Outcomes Data Collection Instrument (PODCI).

Statistical Methods:

Analysis Populations

The following analysis populations are defined for this study:

- The Modified Intent-to-Treat (mITT) Population will include all randomized subjects who receive 1 or more doses of study drug and who contribute any efficacy data to the study.
- The Safety Population will include all subjects who receive 1 or more doses of study drug.
- The PK Population will include all subjects who provide at least 1 quantifiable concentration of ACTH₁₋₂₄ following the administration of at least 1 complete dose of study drug, and without any major protocol deviations that compromise the PK samples.

Sample Size

A total of 132 subjects will be randomized in this study (44 per treatment group). The sample size was determined using the change from baseline in the 10 Meter Walk/Run time. With 37 subjects per treatment group expected to complete the Blinded Treatment Period, the trial will have an 80% power to detect a 1 second treatment difference comparing 2 groups at a significance level of 0.05. Taking into account a dropout rate of approximately 15%, the sample size for this study will be 44 subjects per treatment arm.

Efficacy Analysis

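### Is it a defect that the exposure-response analysis is set at Week 4 when efficacy is judged at Week 24?

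*Combined protocol and SAP*

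**What the plan says.** All of this is in the Combined protocol and SAP, Section 6 (Synopsis).

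- Pharmacokinetic and Pharmacodynamic Evaluations: exposure will be "characterized using population PK modeling with sparse PK sampling implemented in this study". The next sentence is the only readable mention of exposure-response: "The exposure response (selected efficacy and/or safety endpoints at Week 4) relationship will be explored".
- Efficacy Analysis: "The primary efficacy endpoint is a change from baseline in 10 Meter Walk/Run time at Week 24". It is analysed with treatment as factor and baseline as covariate, and the secondary endpoints are handled the same way.
- Pharmacokinetic Analysis: "Population PK analysis for MNK-1411 will be conducted using nonlinear mixed effects modeling". No exposure-response model or endpoint is added.
- Analysis Populations: the PK Population takes "all subjects who provide at least 1 quantifiable concentration of" the peptide after at least one complete dose, provided no major deviation compromises the samples.
- Design and Study Drug: "Subjects will return to the clinic for visits at 4, 8, 12, 16, and 24 weeks after their first dose of study drug", and "No switches in dose are permitted during the Blinded Treatment Period". Dose is banded by weight; the high-dose arm, for example, gets "MNK-1411 0.5 mg (0.5 mL, for subjects weighing more than 20 kg) or 0.4 mg" at or below 20 kg.

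The exploratory objectives are blank in the public text, and the sentence on additional exploratory analyses is redacted.

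**The concern.** Week 4 is 4/24 = one sixth of the way to the visit at which efficacy is judged. If the benefit builds slowly, a Week 4 analysis says little about how exposure drives the Week 24 result. The Week 24 analysis also looks within reach: dose is fixed through the blinded period, Week 24 is a scheduled visit, and a population PK model is planned anyway.

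The apparent loss is information on dose. The primary model compares arms and ignores exposure differences between boys in the same arm. Weight banding creates such differences, because dose steps up by 0.5/0.4 = 1.25 at 20 kg and is otherwise flat, so dose per kg falls with weight inside each band. In a Phase 2 trial with two active doses, that spread could help with dose selection.

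A second worry concerns the PK Population. If a treated boy with low exposure has every sample below the quantification limit, he drops out of that set and exposure summaries shift upward.

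**Working it through.** **1. Does the text contradict itself?** One sentence says an exposure-response relation will be explored for selected endpoints at Week 4. Another sets the primary endpoint at Week 24. They describe different analyses with different purposes and can both be followed. No sentence says the exposure-response analysis supports the primary conclusion, a dose choice or a go/no-go decision. The Week 4 endpoints may also be safety endpoints, for which walk/run timing is beside the point.

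**2. Is a Week 24 analysis known to be absent?** No. The two places where it would naturally appear are blank or redacted, and the readable text ends with the Synopsis. Its absence cannot be counted against the plan.

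**3. Do the plan's own figures hold?** Yes. 37/(1 - 0.15) = 43.5, rounded up to 44 per arm, and 3 x 44 = 132, as stated. The SD is not given. Solving a two-sample t-test for 80% power with 37 per group, a 1 s difference and two-sided 0.05 gives an SD of 1.515 s. Exposure-response enters none of this.

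**4. What would a Week 24 slope test add?** Assumptions: three arms of 37, SD 1.515 s, mean exposure 0, 0.5 and 1.0, effect linear in exposure and 1 s at mean high-dose exposure, lognormal exposure within the active arms, exposure known without error. Results are from simulation.

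| Within-arm exposure CV (assumed) | Power, slope pooled over arms | Power, within-arm exposure only (arm in the model) |
|---|---|---|
| 0% | 80% | none |
| 13% | - | about 9% |
| 30% | 88% | 26% |
| 50% | 93% | 57% |
| 80% | 98% | 88% |

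The 80% in the first row can be checked by hand. The between-arm sum of squares is 37 x [(0 - 0.5)² + (0.5 - 0.5)² + (1 - 0.5)²] = 18.5, and the noncentrality is √18.5/1.515 = 2.84, which is 80% power. So the pooled figure starts from what the randomized doses already supply. Only the last column measures the claimed gain over the arm comparison.

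Within-arm exposure contributes about 37 x CV² x (0.5² + 1²) = 46.25 x CV² to the sum of squares. At CV 30% that is 4.2, against 18.5 from the arms. At CV 80% it is 29.6, so within-arm exposure would then dominate. Which case applies is not in the documents.

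**5. How much spread does weight banding create?** Assume weights uniform over 15-30 kg in the high-dose arm.

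- Range: 400/15 = 26.7 mcg/kg down to 500/30 = 16.7 mcg/kg, a 1.6-fold span.
- Mean: [400 x ln(20/15) + 500 x ln(30/20)]/15 = (115.1 + 202.7)/15 = 21.19.
- Mean square: [400² x (1/15 - 1/20) + 500² x (1/20 - 1/30)]/15 = (2666.7 + 4166.7)/15 = 455.6.
- Variance: 455.6 - 21.19² = about 6.7. SD 2.6, CV 2.6/21.19 = about 12%.

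The low-dose arm has half of each dose and the same CV. That is well below 30-80% and corresponds to about 9% within-arm power. A credible Week 24 analysis would have to adjust for weight, which removes much of this spread.

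**6. Is Week 4 clearly worse?** With 44 per arm and exposure CV 30-80%, pooled power at Week 4 depends on what is assumed:

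| Share of the 1 s effect present | SD 1.515 s | SD 0.75 s (assumed) |
|---|---|---|
| One sixth | 9-13% | 21-37% |
| Half | 40-66% | 93-99% |
| All | 92-99% | - |

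The documents give no time course and no Week 4 SD. The 9% end assumes the effect grows in proportion to time.

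**7. The PK Population.** The readable text gives no sample count, quantification limit or below-limit rule, and does not say that the population model is restricted to that set. The shift is zero if no treated boy has all samples below the limit. There is nothing from which to size a bias.

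**The case for a change.** The best case for acting runs as follows. The Week 4 limit stands in unredacted text, so redaction elsewhere does not remove it. Over 15-30 kg the arms come as close as 16.7 versus 13.3 mcg/kg, a ratio of 1.25, although nominal doses differ 2-fold; dose arm is therefore an imperfect stand-in for dose per kg. A Week 4 analysis informs the Week 24 result only if the effect appears early, and the plan does not say that it does. Extending the analysis would be modelling work, with the Week 4 analysis kept as support.

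The reading of the text stands: the one named analysis does not use the Week 24 endpoint. It also stands that a Week 24 analysis could be informative if within-arm exposure varies widely, as the 88% at CV 80% shows. What does not follow is that the plan is deficient. An exploratory analysis that could be added is not an error when nothing depends on it. The claim that no samples would be needed is also unproven, because the readable text does not say at which weeks PK samples are drawn. Exposure estimated from sparse samples carries error, so the power figures above are optimistic.

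**Conclusion.** The concern does not hold. The Week 4 sentence describes an exploratory analysis that is compatible with a Week 24 primary endpoint, and its scope leaves the primary and secondary tests, the significance level, the power and the sample size as they are. Followed as written, the plan reaches sound conclusions on efficacy.

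The likely gain from a Week 24 exposure-response analysis is uncertain, not demonstrably large. Within-arm power runs from about 9% at an exposure CV of 13% to 88% at 80%, and weight banding by itself supports only the low end. These figures rest on an SD implied by the plan's own 37 per group, 80% power and 1 s, and on assumed exposure distributions, a linear effect, error-free exposure and, for the banding, uniform weights of 15-30 kg. The conclusion does not depend on them, since it follows from the text. The PK Population point is missing detail about a bias that may be zero, in a synopsis that would not be expected to carry it. The conclusion would change only if another part of the protocol rested a dose decision or an efficacy claim on exposure-response; nothing readable does.
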